Transcranial direct current stimulation (tDCS) is a painless, non-invasive, cortical stimulation technique, which is carried out with a battery-driven device, and involves application of electrodes to the scalp, with a weak current flowing between the electrodes, through the brain.(6)

The effects of tDCS on brain function are hypothesized to be neuromodulatory.(6,7) tDCS is believed to be capable of inducing synaptic plasticity through mechanisms of long-term potentiation (LTP) and long-term depression (LTD). At the synaptic level, these changes are believed to be carried out by NMDA receptors of glutaminergic neurons. Therefore, tDCS may

have therapeutic potential for treating dysfunctions of the brain, occurring due to stroke or any other neuropsychiatric pathology, by facilitating recovery-related plastic changes.

The effect of tDCS on aphasia recovery in patients with ischemic stroke has only recently been explored. However, the results have not been consistent and there is still scarcity of data regarding effects of tDCS in stroke.

With this background, we hypothesize that application of tDCS to prespecified areas in the brain would lead to better outcomes in language function, as compared to sham application, in patients with acute ischemic stroke and aphasia.

REVIEW OF LITERATURE

Transcranial direct current stimulation involves the placement of electrodes over the scalp, with the emission of a weak electrical current that flows between the two electrodes. (6,7) The electrodes are themselves named the anode and the cathode. Either one of them can be used for the experiment being conducted, based on the experiment design, in which case the main electrode is known as the target electrode, while the other electrode is known as the reference electrode.

The electrodes can be placed in different montages; some montages place the reference electrode extracephalically, for example on the upper arm, while some montages place the electrodes “bihemispherically” to emit dual stimulation to two parallel cortices (e.g., the parietal cortices— Benwell et al., 2015). (Lindenberg et al., 2010). Various parameters that need to be decided prior to attaching the electrodes are the type of electrodes themselves, the size of the electrodes, the conducting material used, the stimulation duration, current intensity, and ramp up/ramp down times which need to be programmed. (6)

Current flows between the electrodes during stimulation. The current passes through the brain, completing the circuit. Anodal stimulation is believed to depolarise the underlying cortical neurons, thereby making them more sensitive to action potentials and is hence known as “stimulatory”. Cathodal stimulation has the opposite effect, hyperpolarising the underlying cortical neurons, making them less likely to fire, and is thus known as “inhibitory”. (6,7)

Effects of tDCS application can be measured in several ways. The most common method used is via behavioural measures, wherein the researchers aim to measure a given behaviour/activity that would otherwise not be observed under sham conditions.

What makes tDCS a lucrative option for stroke rehabilitation programmes is the fact that it is a non-invasive method. The equipment is reusable, relatively inexpensive, portable, easy to apply, and can allow for reversible modulation of activity in specific brain regions. This has provided an invaluable tool for establishing brain-behavior relationships across a variety of cognitive, motor, social, and affective domains. (8)

So far, tDCS has been used to reduce symptoms of depression (9), it has been shown to reduce hallucinations in schizophrenia(10) and has also been used in autism spectrum disorder (11).

In aphasia rehabilitation, several studies have been undertaken that have utilised tDCS.

Monti et al, in a group comprising of 8 patients of chronic post stroke aphasia, with 4 patients of global aphasia and 4 patients of Broca's aphasia, showed that cathodal tDCS improved naming accuracy in picture naming task. (12)

Hesse et al, in a group comprising of 5 patients with subacute post stroke aphasia, of which 3 patients had global aphasia and 2 patients had Wernicke's aphasia, showed that anodal tDCS improved performance testing on Aachenner aphasia test. (13)

Baker et al, in a group of 10 patients of whom 6 had anomia and 4 had Broca's aphasia, showed that anodal tDCS improved accuracy on picture naming test, and that the benefits lasted for 1 week after treatment. (14)

Kang et al, in a group of 10 chronic aphasia patients, of which 3 had global aphasia, 4 had Broca's aphasia, 2 had anomia and 1 had transcortical aphasia, showed that cathodal tDCS increased accuracy on picture naming task 1 hour after the last session. (15)

Jung et al, in a group of 37 patients, showed that cathodal tDCS improved the aphasia quotient on the Western aphasia battery validated for Korean. (16)

What impedes its use in Stroke rehabilitation, especially its use in aphasia rehabilitation is the lack of comparable research available. Firstly, unlike several studies that examine effects of tDCS on healthy motor physiology, effects on healthy language networks haven't been as thoroughly explored. (17,18,19) Secondly, so far it has been used experimentally in small scale

studies to investigate possible advantages of using tDCS and its possible role in rehabilitation. Since the studies are investigative, there is great variability among the protocols, the sampling and the results; furthermore, only studies with positive results tend to get published, leaving lacunae about methods or protocols that didn't work .

Additionally, across almost all the studies utilising tDCS in aphasia, tDCS hasn't been used in isolation, but has always been used with other rehabilitative measures. As per American Heart Association, "inclusion of behavioral training in the majority of tDCS/aphasia studies may inhibit an understanding of what tDCS does autonomously to language functions." (5) Though one can argue that an aphasia experiment without language training would deprive aphasic subjects of concomitant proven therapy, it might also enable better understanding of tDCS, introducing better paradigms which can then be combined with previously proven methods of rehabilitation.

Finally, studies regarding the use of tDCS in patients with acute stroke with aphasia are also scarce. (20, 21)

In light of the above information, we decided to use anodal tDCS autonomously, in patients with acute ischemic stroke with aphasia.

LACUNAE IN EXISTING KNOWLEDGE

The use of transcranial direct current stimulation (tDCS) for the management of deficits developed in stroke is a relatively new type of management option. Many of the studies performed using tDCS have focused on improvements noted in hemiplegia as compared to aphasia, which is an equally disabling outcome of strokes. The results of these studies have not been conclusive and concordant with each other.

In aphasia management, majority of the studies have focussed on subacute to chronic strokes, and since the use of tDCS is relatively new, the studies have not focussed on a particular type of deficit, or a particular type of stroke. Very few studies have focussed on the impact of solely using tDCS. Very few studies have focussed on acute strokes. The results of the studies have nevertheless, been encouraging.

Improvements in aspects of language tested, after a single session of tDCS, is short lived. There is an unmet need to probe the utility of repetitive tDCS on aspects of language function in patients who are aphasic due to acute stroke. There is also a paucity of data in the Indian scenario regarding the same.

RESEARCH QUESTION

Does transcranial direct current stimulation (tDCS) to prespecified areas of the brain lead to improvement in naming function of aphasic patients with Acute Ischemic Stroke?

RESEARCH HYPOTHESIS

Application of tDCS to prespecified areas in the brain leads to improvement in naming function of aphasic patients with Acute Ischemic Stroke.

AIMS AND OBJECTIVES

AIM: To determine the effect of Anodal Transcranial Direct Current Stimulation on naming function of aphasic patients with Acute Ischemic Stroke.

OBJECTIVES:

Primary Objective: Difference of change in Accuracy between Anodal tDCS group and Sham tDCS group at 5 days on the ICMR Picture Naming Test.

Co-Primary Objective: Difference of change in Reaction Time between Anodal tDCS group and Sham tDCS group at 5 days on the ICMR Picture Naming Test.

Secondary Objectives:

- Difference of change in Correct Response between Anodal tDCS group and Sham tDCS group at 5 days on the ICMR Picture Naming Test.
- Difference of change in PNT Score between Anodal tDCS group and Sham tDCS group at 5 days on the ICMR Picture Naming Test.
- Difference of change in Accuracy between Anodal tDCS group and Sham tDCS group at 4 weeks on the ICMR Picture Naming Test.
- Difference of change in Reaction Time between Anodal tDCS group and Sham tDCS group at 4 weeks on the ICMR Picture Naming Test.
- Difference of change in Correct Response between Anodal tDCS group and Sham tDCS group at 4 weeks on the ICMR Picture Naming Test.
- Difference of change in PNT Score between Anodal tDCS group and Sham tDCS group at 4 weeks on the ICMR Picture Naming Test.

MATERIAL AND METHODS

Place of Study: Department of Neurology, ABVIMS & [name] hospital, New Delhi.

Study design: Randomized, double blinded, sham controlled study.

Sample size: The study of Eun Kyoung Kang, et al observed that post-stimulation response accuracy in tDCS was 31.9 ± 6.9 and in Sham stimulation was 29.9 ± 6.2 . Taking these values as reference, the minimum required sample size with 80% power of study and 5% level of significance is 169 patients in each study group. For finite sample size taking population as 20, total sample size calculated is 19. To reduce margin of error, total sample size taken is 20 (10 per group).

Formula used is:

For comparing mean of two groups

$$N \geq 2(\text{standard deviation})^2 \times (Z\alpha + Z\beta)^2 (\text{mean difference})^2$$

Where $Z\alpha$ is value of Z (normal variate) at two sided alpha error of 5% and $Z\beta$ is value of Z (normal variate) at power of 80% and mean difference is difference in mean values of two groups.

$$\text{Pooled standard deviation} = \sqrt{(S1^2 + S2^2)/2}$$

Where S1 is standard deviation of 1 group. and S2 is standard deviation of other group. Finite population correction factor:-

$$SS \geq n / (1 + [(n - 1)/\text{Pop}])$$

Where Pop is population

Calculations:

$$\text{Pooled standard deviation} =$$

$$= 6.56$$

$$N \geq 2(6.56)^2 \times (1.96 + .84)^2 (2)^2$$

$$\geq 168.66 = 169 (\text{approx.})$$

$$\sqrt{(6.92 + 6.22)/2}$$

So total sample size to be taken is $169 \times 2 = 338$

Finite population correction factor:-

$$SS \geq 338 / (1 + [(338 - 1)/20])$$

$$\geq 18.93 = 19 (\text{approx.})$$

Assuming 20% attrition, each group will consist of at least 12 patients.

Block Randomization

Block Randomization with Sealed Envelope System: - In this technique, patients will be randomized in a series of blocks of 4, using an online randomization generator. Patients will be allocated to either of the groups (group A - true or group B- sham) in a 1:1 ratio. The randomization list will be generated by the biostatistician and transferred to a sealed opaque envelope, and each envelope will be opened by the primary investigator (supervisor) when the corresponding number of eligible participants is enrolled. However, the technician who administers the anodal tDCS procedure will know about the identity of the groups. A blinded investigator will record outcomes. Neither the patient nor the investigator knows which label represents which group, making this a double-blind study.

Study population: Aphasic patients with acute ischemic stroke with left Middle Cerebral Artery territory infarcts.

INCLUSION CRITERIA

- Aphasic patients with left middle cerebral artery territory Acute Ischemic Stroke
- Patients between 18-65 years of age.
- Within 5 days of onset of stroke.

EXCLUSION CRITERIA

- Patients with malignant Middle Cerebral Artery territory infarcts and previous clinical history of cerebral hemisphere stroke.
- Patients with history of previous brain surgery or skull defect due to surgery e.g. craniectomy.
- Patients with epilepsy.
- Patients with history of significant head trauma in the last 1 month.
- Patients with documented history of major depression prior to stroke.
- Patients with alcohol/drug abuse in the past 6 months.
- Patients with prior significant cognitive impairment.
- Pacemaker in-situ, cochlear implant in-situ.
- Pregnancy.

PROCEDURAL DETAILS

- All consenting patients recruited for the study will be evaluated clinically in detail. The patients will undergo aphasia testing using the Western Aphasia Battery and will be classified accordingly into the subtypes of aphasia. The patients will then be randomized into either the true stimulation group or the sham stimulation group as mentioned.

Picture Naming Test

- The Indian Council of Medical Research (ICMR) validated the Picture Naming Test (PNT), part of the ICMR MUDRA Toolbox for use in patients with Dementia. The PNT was used to objectively quantify Naming ability during and after sessions of anodal Transcranial Direct Current Stimulation. The ICMR PNT has been validated in five languages, including English and Hindi.
- The ICMR PNT consists of 30 line drawings.
- The administration of the test is as follows:
 - The pictures are shown one by one.
 - The subject has to identify each item by telling the first name that comes to their mind upon seeing the stimulus. 10 seconds are given for an unprompted response.

- If the subject is unable to name the image shown or makes an error during naming, cues are provided.
 - First, a category/semantic cue is provided, and the patient is given 10 seconds to name the picture.
 - If the subject fails to respond or responds incorrectly, a phonemic cue is provided, and the subject is again given 10 seconds to respond.
 - If the subject is still unable to respond or makes an error, the test moves on to the next picture.
 - Hence, the maximum time for naming an image is 30 seconds.
 - Care is taken that the entire test be conducted in the same language.
- Additionally, scoring is done based on the prespecified names provided. A few objects shown in the pictures may have more than one name, but the response accepted is the response prespecified in the validated PNT.

The scoring for the ICMR PNT is as follows:

- Correct response in the testing language spontaneously (without cues) (NL)= +3
- Correct response in testing language with a semantic cue (NL) = +2
- Correct response in testing language with a phonemic cue (NL) = +1
- If the responses are given in another language, and not the testing language, the scores are marked as follows:
 - Correct response in the testing language spontaneously (without cues) = OL3
 - Correct response in testing language with semantic cue = OL2
 - Correct response in testing language with phonemic cue = OL1
- Total correct responses are calculated as NL + OL.
- If the subject makes an error in naming, it is marked as ER. If the subject is unable to name, the scoring is done as 0.

For the purpose of our study:

- The instructions provided for administering the PNT, as laid down by the ICMR, will be followed for scoring correct responses. Since all patients tested will have Hindi as their native language, there will be no OL responses.

- Additionally, response times were noted for each picture named. If the patients could not name the pictures even after providing both semantic and phonemic cues, a response time of 30 seconds was noted. A calibrated stopwatch was used for marking the response times.

The ICMR PNT will be performed on:

- Day 0 (i.e. the day anodal tDCS/sham tDCS sessions were initiated, before the first session of anodal tDCS).
- Day 1 (i.e. 1 day after the first session of anodal tDCS/sham tDCS, before the second session).
- Day 5 (i.e. after 5 sessions of anodal tDCS/sham tDCS).
- 1 week +/- 2 days after the last session of anodal tDCS/sham tDCS, to look for the persistence of benefit, if any.
- 4 weeks +/- 2 days after the last session of anodal tDCS/sham tDCS, to look for the persistence of benefit, if any.

The various parameters assessed in the study using the ICMR-PNT are defined as follows:

- Accuracy is defined as the number of words spoken without the help of a semantic or phonemic cue on the ICMR Picture Naming Test
- Correct Response is defined as the total number of words spoken, with or without the help of either a semantic or a phonemic cue on the ICMR Picture Naming Test.
- PNT scores will be calculated for all the correct responses provided. The guidelines provided for the use of ICMR–PNT will be used. A response obtained without any semantic or phonemic cue is scored as 3. A response obtained with a semantic cue is scored as 2. A response obtained using both semantic and phonemic cues is scored as 1. No response obtained is scored as 0.
- A stopwatch will be used to record the reaction times of the patient during the process of naming items on the PNT. Timings, as suggested by the ICMR-PNT guidelines, will be used. 10 seconds will be provided for the patient to name the picture without any semantic or phonemic cues. At the end of 10 seconds, the stopwatch will be paused, a semantic cue provided, and the patient then continued to be timed. At the end of the next 10 seconds, the

stopwatch will be paused again, a phonemic cue provided, and the patient then continued to be timed. A total of 30 seconds will be provided per picture for naming. Patients will be timed as per their responses with or without cues. Reaction time will be noted as 30 seconds if the patient fails to name the picture after both semantic and phonemic cues.

tDCS Parameters:

- Stimulation site: left Brodmann area 45 (Broca's area) localized based on the 10-20 system of electroencephalography. On the tDCS equipment, the montage created using the leads Fp2 and F3 corresponds to maximal stimulation of Brodmann area 45.
- Reference electrode: Right supraorbital area (Fp2).
- Electrode size: Gel electrodes.
- Intensity of stimulation provided: 2mA.
- Duration of stimulation provided: 20 minutes, with ramp up & ramp down of 10 seconds each. Patients undergoing sham stimulation will receive stimulation for the first and last 10 seconds of 20 minutes period.
- Number of sessions: 5 sessions in 1 week.
- Task performed for assessment: ICMR Picture Naming test. (detailed above)

The tDCS procedure will be conducted as follows:

- The patients preferably seated in a chair. If the patients have evidence of dense hemiplegia with difficulty sitting in a chair or wheelchair, the sessions will be conducted with the patients in the semi-recumbent position to prevent dislodgement of the tDCS equipment during the sessions.

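### The 169 per group rests on post-stimulation scores of unstated unit that cannot be this trial's Accuracy counts, and on a level SD rather than an SD of change, so it is unsupported for the primary endpoint

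*Protocol*

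**What the plan says.** In the Protocol, the sample size paragraph of Material and Methods takes its planning values from a cited naming study: "post-stimulation response accuracy in tDCS was 31.9 ± 6.9 and in Sham stimulation was 29.9 ± 6.2". No unit or maximum score is given. From these it concludes that "the minimum required sample size with 80% power of study and 5% level of significance is 169 patients in each study group", using the usual formula for two means with two-sided alpha, and the pooled SD of the two post-stimulation values. A finite-population step then brings the total down to 20.

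The primary objective (Aims and Objectives) is a different quantity: "Difference of change in Accuracy between Anodal tDCS group and Sham tDCS group at 5 days on the ICMR Picture Naming Test".

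Under Procedural Details, Picture Naming Test, "The ICMR PNT consists of 30 line drawings", and Accuracy is defined there as the number named without a semantic or phonemic cue. It therefore lies between 0 and 30.

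The Review of Literature says of the same cited study, in 10 chronic aphasia patients, that it "showed that cathodal tDCS increased accuracy on picture naming task 1 hour after the last session". This trial gives anodal stimulation to patients within 5 days of stroke onset.

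**The concern.** A sample size calculation has to use the effect and the variability of the endpoint that will be analysed. Two things do not match here. The borrowed mean of 31.9 lies above the highest possible value of Accuracy, so the values are in some other unit or from some other score. The borrowed SDs describe scores after stimulation, whereas the endpoint is a change from baseline.

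The section nonetheless presents 169 per group at 80% power as the requirement. A reader would take it that the trial was planned around a gain of two pictures on this test with a known SD, and the protocol supports neither. The figure would also mislead anyone who removed the finite-population step and fell back on 169 as the proper target.

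**Working it through.** **Inputs.** From the sample size section: means 31.9 and 29.9, SDs 6.9 and 6.2, two-sided 5%, 80% power, 1:1 allocation, and 10 per group as adopted. From the Picture Naming Test section: 30 pictures. Not given anywhere: the unit of the cited values, any SD of change, or the correlation between Day 0 and Day 5 scores.

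**1. The protocol's own figure.** Pooled SD = √[(6.9² + 6.2²)/2] = √43.025 = 6.56. Then n per group = 2 × 43.025 × (1.96 + 0.84)² / 2² = 2 × 43.025 × 7.84 / 4 = 168.66, so 169. The stated figure reproduces, and the standardised effect is 2/6.56 = 0.305. The arithmetic is sound; the question is whether the inputs apply.

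**2. Scale.** Accuracy has a maximum of 30, and 31.9 > 30, so 31.9 is not an Accuracy count. It could be a percentage, or a score with a wider range. If it were a percentage (an assumption), the values would correspond to 31.9 × 0.3 = 9.6 and 29.9 × 0.3 = 9.0 pictures, a difference of 0.6 of a picture with an SD of 6.56 × 0.3 = 1.97. The ratio 0.6/1.97 is still 0.305, so n would still be 169. The scale mismatch removes the reading of 2 points as 2 pictures; it does not by itself change n.

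**3. Level versus change.** Assume the same SD at Day 0 and Day 5 and a correlation ρ between them. Then SD of change = 6.56 × √[2(1 − ρ)]. Keeping the 2-point difference in the source unit, n per group = 168.66 × 2(1 − ρ):

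| ρ (assumed) | SD of change (source unit) | n per group |
|---|---|---|
| 0 | 9.28 | 337.3 → 338 |
| 0.5 | 6.56 | 168.7 → 169 |
| 0.8 | 4.15 | 67.5 → 68 |
| 0.9 | 2.93 | 33.7 → 34 |

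Under the equal-SD assumption, 169 is the right figure for a change score only at ρ = 0.5, a value the protocol does not state. The range spans a factor of about ten (338/34).

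**4. What the adopted sample can detect.** With 10 per group, 80% power and two-sided 5%, a two-sample t calculation gives a detectable difference of about 1.32 SDs of change. The protocol's normal formula gives 2.8 × √(2/10) = 1.25. Either can be turned into pictures only once an SD of change on the 0–30 count has been assumed.

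**The case against.** Much can be said for the protocol, and several stronger readings have to be given up.

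- *A reader might infer that 31.9 is impossible on a 30-picture test.* That goes too far. The same test also yields the weighted PNT score, which reaches 30 × 3 = 90, and 31.9 could be a percentage. Only the uncued count, which is the primary endpoint, is capped at 30.
- *A reader might infer that the wrong scale makes 169 wrong.* It does not: a linear rescaling leaves the standardised effect and n unchanged.
- *A reader might infer that post-stimulation means give the wrong difference.* With randomised groups the expected baselines are equal, so the expected difference in post-scores equals the expected difference in change. Only the SD is affected.
- *A reader might infer that 169 is too large, or too small.* The documents do not show which. With equal SDs it is too large if ρ exceeds 0.5 and too small if ρ is below 0.5. With unequal SDs, which are plausible so soon after a stroke, even that threshold moves.
- *A reader might convert the detectable difference to pictures using 6.56.* That would reuse an SD whose unit is unknown.

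The polarity and stage differences are the weakest part. The Review of Literature discloses both, the protocol says openly that acute-stroke data are scarce, and borrowing from an imperfect study is common. The fair criticism is that no reason is given for the transfer, not that it is an error.

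Finally, 169 is not the size used. Passing the totals implied by the table, 68 to 676, through the protocol's finite-population formula gives 68/(1 + 67/20) = 15.6 to 676/(1 + 675/20) = 19.5, or 16 to 20 patients. Better inputs would hardly alter enrolment as planned. That step is a separate and larger problem, and it does not make the inputs valid.

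**Conclusion.** The point holds in limited form. The planning values have no stated unit and cannot be Accuracy counts, so the effect cannot be read as 2 pictures. The SD used is that of a level, while the endpoint is a change, and no SD of change is given. The 169 per group is therefore unsupported for the primary endpoint, with the direction of error unknown. The illustrative range of 34 to 338 per group rests on three assumptions: a 2-point difference in the source unit, an SD of 6.56 at both visits, and ρ between 0 and 0.9. No single corrected figure can be derived from the protocol. The use of a cathodal study in chronic patients without justification is a secondary point; the scale and SD mismatches carry the conclusion without it.

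**What to change.** Rewrite the sample size paragraph:

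- Stop presenting 169 per group and 80% power as derived for the primary endpoint.
- Name the planning quantity as the SD of the Day 0 to Day 5 change in the 0–30 Accuracy count. Label it an assumption and show a range, including the SDs at each visit and the correlation behind it.
- Report what the actual sample can detect: about 1.32 SDs of change at 10 per group (80% power, two-sided 5%, t-based). Convert to pictures only under the stated SD.
- If the reference study is kept, state its unit, its polarity and disease stage, that its values are post-stimulation scores, and why it is thought to carry over to anodal stimulation in acute stroke.

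The cost is one paragraph of text. No more patients, visits or measurements are needed for this point.

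### The finite-population correction that cuts 338 patients to 19 does not apply to a randomised comparison, so the 80% power calculation does not support 20 to 24 patients

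*Protocol*

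**What the plan says.** The Sample size paragraph takes its inputs from a published picture-naming study, in which "post-stimulation response accuracy in tDCS was 31.9 ± 6.9 and in Sham stimulation was 29.9 ± 6.2". From these it concludes that "the minimum required sample size with 80% power of study and 5% level of significance is 169 patients in each study group", and doubles this to 338. The formula notes state that alpha is two-sided.

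It then introduces a finite population correction, SS = n/(1 + (n − 1)/Pop): "For finite sample size taking population as 20, total sample size calculated is 19". The next step is "To reduce margin of error, total sample size taken is 20 (10 per group"), followed by "Assuming 20% attrition, each group will consist of at least 12 patients".

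No source or reason is given for a population of 20, and power is not restated at 20 or 24 patients. Under Block Randomization, allocation is 1:1 to true or sham stimulation. Under Aims and Objectives, the primary objective is the between-group difference in change in Accuracy at 5 days.

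**The concern.** A finite-population correction is valid when a descriptive quantity, such as a mean or a proportion, is estimated for a fixed and enumerable population by sampling without replacement. Uncertainty then shrinks as the sample approaches the whole population. A randomised comparison is different. Its question is whether stimulation improves naming in aphasic patients with acute ischaemic stroke, and the protocol defines its study population by clinical criteria, not as a list of 20 people. Enrolling all of some notional 20 patients would not remove the patient-to-patient variability that drives the error of the treatment difference.

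The corrected figure of 19 therefore carries no information about power. If it stands, the trial appears to be sized by an 80% power calculation when its size was in effect fixed by the choice of 20 as the population. Anyone judging the trial's worth, or later reading its result, would be working from a power figure that does not belong to it.

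**Working it through.** **Inputs, all from Sample size:** means 31.9 and 29.9 (difference 2.0); SDs 6.9 and 6.2; two-sided alpha 5% (Z = 1.96); power 80% (Z = 0.84); Pop = 20; 20% attrition.

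**1. The protocol's figures reproduce.**
- Pooled SD = √((6.9² + 6.2²)/2) = 6.559, printed as 6.56.
- n per group = 2 × 6.559² × (1.96 + 0.84)² / 2² = 168.66, so 169; total 338.
- Correction: 338 / (1 + 337/20) = 338 / 17.85 = 18.94, so 19.

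The arithmetic is right. The fault lies in using the second formula at all.

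**2. What the correction does with Pop = 20.** Rearranged, n/(1 + (n − 1)/20) = 20n/(n + 19), which is below 20 for every n.

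| n entered | Result |
|---|---|
| 50 | 14.5 |
| 338 | 18.9 |
| 1,000 | 19.6 |
| 1,000,000 | 20.0 (rounded) |

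Keeping n = 338 and changing the assumed population to 50, 100, 200 or 1,000 gives about 44, 77, 126 or 253. The answer follows the chosen population, not the power requirement. The attrition step also asks for at least 24 patients, more than the assumed population of 20.

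**3. Power on the protocol's own inputs.** Two-sided 5% t-test, noncentral t, standardised effect d = 2/6.559 = 0.305, SE = 6.559 × √(2/n).

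| Per group | SE | Noncentrality 2/SE | Power |
|---|---|---|---|
| 10 | 2.93 | 0.68 | 9.9% |
| 12 (no losses) | 2.68 | 0.75 | 11.0% |
| 169 | 0.71 | 2.80 | 79.8% |

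The normal approximation gives 10.1%, 11.3% and 80.0%.

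**4. Allowing for change scores.** The SD of 6.56 belongs to post-stimulation scores, while the primary endpoint is change. The protocol gives no baseline correlation r, so a range is assumed, with equal SDs at both times: SD of change = 6.559 × √(2(1 − r)).

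| Assumed r | SD of change | Power at 10 per group |
|---|---|---|
| 0.5 | 6.56 | 9.9% |
| 0.7 | 5.08 | 13% |
| 0.8 | 4.15 | 18% |
| 0.9 | 2.93 | 30% |

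Reaching 80% at 10 per group would need an SD of change of about 1.5, which means r of about 0.97.

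**5. Detectable effect at 80% power (t-test).** d = 1.32 at 10 per group and 1.20 at 12, against the 0.305 planned. The standardised scale is used because Accuracy counts uncued correct names on a 30-picture test, so it cannot exceed 30, whereas the reference mean is 31.9. The reference scores must lie on another scale.

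**The case against.** The strongest reply is that the protocol attaches 80% power to 169 per group and never says outright that 20 patients achieve it. That is literally correct. A reader might infer an explicit claim of 80% power at 20 patients, and the text does not contain one. What stands is the implication: 80% is the only power quoted, and 19 is presented as the corrected result of that same calculation.

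A second reply is that 10% is conditional. This also stands. The planning SD is for post-stimulation scores and the endpoint is change, so 10% is exact only for the printed inputs, or for a baseline correlation near 0.5. A reader might infer that the trial's real power is 10%, so that a true effect would be missed nine times in ten; the protocol does not give the figures needed to say that. The assumed range of 10% to 30% is still far short of 80%.

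A third reply is that figures on the reference scale are not this trial's points. Correct: converting the detectable difference into picture-naming points is tempting but unsupported, given the 30-item ceiling. The objection also reaches the 338, which can be presented only as what the printed inputs require.

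Finally, one might say that this is a small feasibility trial and should be judged as such. The protocol neither calls itself a pilot nor gives feasibility as the reason for 20. Nor does it say how a non-significant result would be read, so a prediction that it would be misread goes beyond the text.

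**Conclusion.** The concern holds as a misapplied method, not as an arithmetic slip. The finite-population correction has no place in sizing this randomised comparison, and nothing else in the protocol justifies 20 to 24 patients against a derived requirement of 338. The implied 80% power is not delivered. On the protocol's own inputs power is about 10% at 10 per group and 11% at 12; on change scores it is about 10% to 30% at 10 per group, assuming equal SDs and baseline correlations of 0.5 to 0.9. The smallest effect detectable with 80% power is a d of about 1.3 at 10 per group or 1.2 at 12, roughly four times the planned 0.305.

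The documents do not support going further, whether to a single true power figure, to a detectable difference in test points, or to an assumed feasibility motive. The conclusion that the correction is inapplicable depends on none of these.

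**What to change.** In Sample size:

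- Delete the finite-population correction and any implication that 19 to 24 patients give 80% power.
- State that 338 evaluable patients is what the protocol's own inputs require. Give the actual power at 10 to 12 per group on those inputs, with the assumption made about change scores.
- Give the sponsor's true reason for 20 to 24 patients.
- Express the detectable effect as a standardised difference (about 1.3 at 10 per group, 1.2 at 12), not in picture-naming points.
- Present the trial as a pilot or estimation study that reports the between-group difference with its 95% confidence interval.

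The cost is protocol wording only, with no extra patients. The drawback is that the stated power becomes much less favourable.
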